### 4.4 Permissible and Prohibited Medications/Treatments

#### 4.4.1 Permissible Medications/Treatments

Medications that are not specifically prohibited in [Section 4.4.2](#) are allowed, with the following clarifications and restrictions.

The following medications for the acute treatment of migraine are allowed during the study:

- Any triptan
- Any ergot derivative
- Any opioid
- Any other form of analgesic (including acetaminophen)
- Any NSAID agent
- Any antiemetic agent

Aspirin up to 325 mg/day is allowed for cardiac prophylaxis.

SSRI or SNRI will be permitted, provided that treatment is stable for at least 60 days prior to Visit 1 and continues without change in dose throughout the study.

Therapy considered necessary for the participant's welfare may be given at the discretion of the investigator. If the permissibility of a specific medication/treatment is in question, please contact Allergan.

#### **4.4.2 Prohibited Medications/Treatments**

The following medications are prohibited 30 days prior to Visit 1 (unless otherwise indicated) for all participants and throughout the study (see [Attachment 12.1](#)):

- Strong and moderate CYP3A4 inhibitors, including but not limited to: systemic (oral/IV) itraconazole, ketoconazole, fluconazole, erythromycin, clarithromycin, telithromycin, diltiazem, verapamil, aprepitant, cyclosporine, nefazodone, cimetidine, quinine, and HIV protease inhibitors
- Strong and moderate CYP3A4 inducers, including but not limited to: barbiturates (eg, phenobarbital and primidone), systemic (oral/IV) glucocorticoids, nevirapine, efavirenz, pioglitazone, carbamazepine, phenytoin, rifampin, rifabutin, and St. John's wort
- Strong OATP1B1 inhibitors (eg, gemfibrozil)
- Drugs with narrow therapeutic margins with theoretical potential for CYP drug interactions (eg, warfarin)
- Medications with demonstrated efficacy for the prevention of migraine (eg, amitriptyline, topiramate, propranolol). See [Attachment 12.2](#)
- CBD oil

- Therapeutic or cosmetic botulinum toxin injections (eg, Dysport®, BOTOX®, Myobloc®, Xeomin®, Jeuveau™) into areas of the head, face, or neck within 6 months prior to Visit 1 and for the duration of the study
- Injectable monoclonal antibodies blocking the CGRP pathway (eg, Aimovig™, Emgality™, Ajovy®) within 6 months prior to Visit 1 and for the duration of the study

The decision to administer a prohibited medication/treatment is done with the safety of the study participant as the primary consideration. When possible, Allergan should be notified before the prohibited medication/treatment is administered.

#### **4.4.3 Definition of Women of (Non-)Childbearing Potential and/or Acceptable Contraceptive Methods**

For purposes of this study, women will be considered of childbearing potential unless they are naturally postmenopausal (ie, no menses for 2 years) or permanently sterilized (ie, bilateral tubal ligation, bilateral tubal occlusion [eg, Essure® placement with HSG confirmation], bilateral salpingectomy, bilateral oophorectomy, or hysterectomy). For women of child-bearing potential who may participate in the study, the following methods of contraception, if properly used, are generally considered highly effective:

- Combined (estrogen and progestogen containing) hormonal contraception such as oral, intravaginal, or transdermal (ie, pill, vaginal ring, patch)
- Progestogen-only hormonal contraception (with inhibition of ovulation) that are oral, injectable, or implantable
- IUD or IUS
- Vasectomized partner (provided that the partner is the sole sexual partner of study participant and that the vasectomized partner has received medical assessment of the surgical success)
- Sexual abstinence (defined as refraining from heterosexual intercourse for the duration of the study)

Acceptable birth control methods which may not be considered as highly effective:

- Progestogen-only oral hormonal contraception (where inhibition of ovulation is not the primary mode of action)
- Male or female condom with or without spermicide (female and male condoms should not be used together)

- Cap, diaphragm or sponge with spermicide
- A combination of male condom with either cap, diaphragm or sponge with spermicide (double barrier methods) are also considered acceptable, but not highly effective, birth control methods

For males who may participate in the study, the following methods of contraception, if properly used, are generally considered reliable: post-bilateral vasectomy, barrier contraception or sexual abstinence. Male participants must also refrain from donating sperm during the course of the study.

The investigator and each participant will determine the appropriate method of contraception for the participant during participation in the study.

If a woman becomes pregnant during the study, the investigator will notify Allergan immediately after the pregnancy is confirmed and the participant will be discontinued from the study after appropriate safety follow-up. The investigator will (1) notify the participant's physician that the participant was being treated with atogepant (2) follow the progress of the pregnancy. The investigator must document the outcome of the pregnancy and provide a copy of the documentation to Allergan.

#### **4.4.4 Special Diet or Activities**

Participants should refrain from consuming grapefruit or grapefruit juice from the time the ICF is signed until completion of the study. Participants should also refrain from making significant changes to their diet or caffeine intake during the study.

Alcohol intake should be limited to no more than 1 drink per day throughout the study. A drink is defined as a 12-ounce can/bottle of beer, a 4-ounce glass of wine, or 1 ounce of liquor.

#### **4.5 Screen Failures**

Screen failures are defined as participants who consent to participate in the study but are not subsequently treated.

### **5 Study Intervention**

#### **5.1 Study Intervention and Formulations**

Tablets containing atogepant 60 mg (Formulation Number: 11281X)

## 6 Control Intervention

Not applicable.

### 6.1 Methods for Masking/Blinding

This is an open-label study.

### 6.2 Treatment Allocation Ratio

All participants will be treated with atogepant 60 mg once daily.

### 6.3 Method for Assignment to Treatment Groups

Prior to initiation of atogepant in this open-label extension study, each participant who provides informed consent will maintain their lead-in study participant number. This number will serve as the participant identification number on all study documents.

At Visit 1, eligible participants will receive atogepant 60 mg once daily.

Before the study is initiated, log-in information and directions for the IWRS will be provided to each site.

The atogepant bottles will be labeled with kit numbers. The IWRS system will provide the site with the specific medication kit number(s) for each participant at Visit 1. Sites will dispense atogepant according to the IWRS instructions. Sites will also log onto the IWRS at subsequent visits to obtain a kit number for dispensing atogepant. Sites will receive the IWRS confirmation notifications for each transaction. All notifications are to be maintained with the study source documents.

Atogepant bottles will be dispensed at the study visits summarized in the Schedule of Visits and Procedures. Returned atogepant bottles should not be re-dispensed to the participants.

### 6.4 Treatment Regimen and Dosing

Participants who meet all of the study entry criteria at Visit 1 will be treated with atogepant 60 mg once daily.

Atogepant to be used in this trial is listed in [Table 6-1](#).

Participants will be instructed to take their atogepant at approximately the same time each day. Atogepant will be administered orally for 40 weeks, and participants will be followed for 4 weeks following completion or discontinuation of the atogepant.

**Table 6-1. Study Intervention**

Drug/Dose	Study Intervention Frequency	Route of Administration
Atogepant 60 mg	Once daily	Oral

## 6.5 Safety Measures

### 6.5.1 Adverse Events

AEs will be collected from the time of consent through the last visit. For all AEs, the investigator must provide an assessment of the severity, causal relationship to the investigational product, start and stop date, seriousness of the event (eg, SAE), document all actions taken with regard to the study or control intervention, and detail any other treatment measures taken for the AE. For events noted as SAEs, Allergan must be notified immediately to meet their reporting obligations to appropriate regulatory authorities.

### 6.5.2 Adverse Events of Special Interest

Selected non-serious and SAEs are of special interest (AESI) and will require immediate reporting, recording, and follow-up. The following events will be closely monitored:

- Treatment-emergent suicidal ideations with intent, with or without a plan, (ie, Type 4 or 5 on the C-SSRS) or any suicidal behaviors
- Treatment-emergent elevated ALT or AST laboratory value that is  $\geq 3 \times$  ULN
- Potential Hy's law cases: elevated ALT or AST laboratory value that is  $\geq 3 \times$  ULN and an elevated total bilirubin laboratory value that is  $\geq 2 \times$  ULN and, at the same time, an alkaline phosphatase laboratory value that is  $< 2 \times$  ULN.

Reporting requirements for AESI, ALT or AST elevations, and potential Hy's law cases are outlined in [Sections 9.5](#) and [9.5.1](#). These AEs or events determined to be SAEs must be reported appropriately via the designated eCRFs and safety forms.

### 6.5.3 Clinical Laboratory Determinations

Blood and urine samples for clinical laboratory tests will be collected at the visits outlined in [Table 1](#). Hematology, chemistry, INR, and urinalysis will be conducted at these visits. Serology and the urine drug screen will only be conducted at Visit 1. The investigator will assess the clinical significance of any values outside the reference ranges provided by the central laboratory. Participants with abnormalities judged to be clinically significant, laboratory values that meet exclusionary criteria, or positive results on the urine drug screen at Visit 1 will be

withdrawn from the study. Women of childbearing potential will be required to have a urine pregnancy test at all visits. A positive pregnancy test at Visit 1 will exclude the participant from the study.

Investigators may also perform unscheduled clinical laboratory determinations at any time for the purpose of participant safety.

Participants are not required to fast overnight before coming in for their appointments.

The clinical laboratory parameters to be measured are shown in Table 6–2.

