**Table 6–2. Clinical Laboratory Parameters**

Category	Parameter
Chemistry	Sodium, potassium, chloride, bicarbonate, glucose, blood urea nitrogen, creatinine, total bilirubin, alkaline phosphatase, aspartate aminotransferase, alanine aminotransferase, lactate dehydrogenase, creatine kinase, total protein, albumin, calcium, phosphorus, uric acid, total cholesterol. The estimated glomerular filtration rate will be calculated by the central laboratory
Hematology	Hemoglobin, hematocrit, red blood cell count, red blood cell indices (mean corpuscular volume, mean corpuscular hemoglobin, mean corpuscular hemoglobin concentration), white blood cell count, including differential (neutrophils, lymphocytes, monocytes, eosinophils, and basophils), platelet count
Urinalysis	Urine dipstick for specific gravity, pH, protein, glucose, ketones, bilirubin, and blood; microscopic examination including red blood cells/high-power field, white blood cells/high-power field, and casts/low-power field
Coagulation	INR
Serology	At Visit 1 only: anti-hepatitis A IgM antibody, hepatitis B surface antigen, anti-hepatitis C antibody, anti-hepatitis E IgM antibody
Urine Drug Screen	Screening for drugs of abuse (eg, marijuana, cocaine, phencyclidine, amphetamines, benzodiazepines, barbiturates, opiates) will be conducted using a urine drug screen at Visit 1. Those with a positive result on the Visit 1 urine drug screen for recreational (including marijuana regardless of legality) or illicit drugs or non-disclosed concomitant medications are not allowed to be repeated. For all other positive results, the urine drug screen may be repeated with permission from Allergan; a negative result or an explanation of a positive result due to concomitant medication use (eg, opioids prescribed for migraine pain) will be required for study participation.

IgM = immunoglobulin M; INR = International Normalized Ratio

A central laboratory will be used to evaluate all urine and blood samples, which will be collected, processed, and stored according to the instructions provided by the laboratory.

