## 8.9 Withdrawal Criteria

- **Participants with the following at Visit 1:**
  - **Laboratory Results:**
    - ALT or AST > 1 x ULN OR
    - total bilirubin > 1 x ULN (except for participants with a diagnosis of Gilbert's disease) OR
    - serum albumin < 2.8 g/dL
    - Positive result on the urine drug screen unless explained by concomitant medication use (eg, opioids prescribed for migraine pain).
    - Positive result on anti-hepatitis A IgM antibody, hepatitis B surface antigen, anti-hepatitis C antibody testing, or anti-hepatitis E IgM antibody.
  - **ECG Results:**
    - QTcF > 450 msec for males and QTcF > 470 msec for females on the final central vendor ECG report
    - Clinically significant cardiac rhythm or conduction abnormalities (eg, atrial fibrillation, second- or third-degree heart block)
- **Participants with the following at any study visit:**
  - Female participants who become pregnant ([Section 9.4](#))
  - Participants who meet atogepant discontinuation criteria related to abnormal liver function tests ([Section 9.5](#)), and advised not to be rechallenged, will be withdrawn from the study and should refrain from taking atogepant.
  - Participants who reply with “yes” to questions 4 or 5 in the suicidal ideation section or “yes” to any question in the suicidal behavior section of the C-SSRS at Visits 2 through 10 must be withdrawn from the study.
  - A participant with a condition and/or a situation that, in the investigator's opinion, may put the participant at significant risk, may confound the study results, or may interfere significantly with the participant's participation in the study may be withdrawn from treatment.

All withdrawn participants should receive appropriate follow-up as in routine clinical practice, including the ET (Visit 11) and the EOS (Visit 12) assessments.

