**Atogepant must be discontinued if any of the following criteria are met:**

- ALT or AST  $\geq 3 \times$  ULN and the participant is symptomatic with the appearance of fatigue, nausea, vomiting, right upper quadrant pain or tenderness, fever, rash, or eosinophilia ( $> 5\%$ )
- ALT or AST  $\geq 3 \times$  ULN and total bilirubin  $> 2 \times$  ULN
- ALT or AST  $\geq 3 \times$  ULN and INR  $> 1.5$
- ALT or AST  $\geq 5 \times$  ULN for more than 2 weeks
- ALT or AST  $\geq 8 \times$  ULN

The participant may be rechallenged with atogepant only after consultation with the Allergan Medical Monitor. For participants who are not rechallenged, the participant should be discontinued from the study and complete an ET Visit and an EOS Visit 4 weeks later. Participants should receive appropriate follow-up as per standard of care.

**The investigator must contact the Allergan Medical Monitor to discuss all cases of confirmed ALT/AST elevation  $\geq 3 \times$  ULN. All ALT/AST elevations must be followed until ALT and AST return to  $< 1.5 \times$  ULN and there is full clinical resolution.**

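### Protocol 6.5.3 withdraws every participant with a positive Visit 1 drug screen, while 8.9 and Table 6-2 allow explained positives; its laboratory trigger also leaves the visit scope unclear

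*Protocol*

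**What the plan says.** Section 6.5.3 contains one sentence with three triggers and one mandatory consequence. The triggers read "Participants with abnormalities judged to be clinically significant, laboratory values that meet exclusionary criteria, or positive results on the urine drug screen at Visit 1". The consequence, stated without exception, is that all of these are to be "withdrawn from the study". The sentence before it is not tied to any visit: "The investigator will assess the clinical significance of any values outside the reference ranges provided by the central laboratory".

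Other parts of the protocol cover the same ground:

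- **Section 8.9, Visit 1 list.** The drug-screen ground for withdrawal reads "Positive result on the urine drug screen unless explained by concomitant medication use (eg, opioids prescribed for migraine pain"). The same list holds numeric limits for ALT/AST, total bilirubin and albumin, and the serology results.
- **Section 8.9, any-visit list.** A participant who meets the Section 9.5 stopping criteria is withdrawn if advised not to be rechallenged. A separate clause, based on the investigator's opinion, is discretionary and refers to leaving treatment.
- **Table 6-2.** Recreational, illicit or non-disclosed positives may not be repeated. Then: "For all other positive results, the urine drug screen may be repeated with permission from Allergan". The condition for taking part is that "a negative result or an explanation of a positive result due to concomitant medication use (eg, opioids prescribed for migraine pain) will be required".
- **Section 4.4.1.** "The following medications for the acute treatment of migraine are allowed during the study", and the list that follows includes any opioid.
- **Section 9.5.** ALT or AST at or above 3 x ULN after dosing leads to a retest and, if confirmed, close follow-up. Five criteria are listed under "Atogepant must be discontinued if any of the following criteria are met". Rechallenge is possible after consultation with the Medical Monitor.

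**The concern.** A withdrawal rule should give one answer for one result. For a positive screen explained by a disclosed, permitted medicine, the prose of 6.5.3 requires withdrawal, while 8.9 and Table 6-2 let the participant stay. The laboratory triggers in the same sentence raise a second question, because their visit scope depends on how far the Visit 1 qualifier reaches.

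Safety and tolerability are the only objective, and there is no control arm. Atogepant is dispensed at Visit 1 (Section 8.4.1.1), and 8.9 treats Visit 1 laboratory results as grounds for withdrawal. A participant who has taken a dose before being withdrawn is in the Safety Population (SAP 6.2) and counts in the premature-discontinuation summaries (SAP 7.0). One withdrawn before dosing is a screen failure (Section 4.5). One who is kept contributes exposure. If the wider reading of 6.5.3 were applied, it would also decide who is observed on continued drug after a laboratory abnormality.

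**Working it through.** The plan gives no figure to reproduce. The check is to take one result at a time and compare what each section does with it, under two readings of 6.5.3:

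- **Reading A:** the Visit 1 qualifier limits only the drug-screen trigger.
- **Reading B:** it limits all three triggers.

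| Case | 6.5.3 | Other sections | Conflict? |
|---|---|---|---|
| 1. Visit 1 screen positive, explained by a prescribed opioid | Withdraw | 8.9: keep. Table 6-2: keep | Yes, under A and B |
| 2. Visit 1 screen positive, not recreational, illicit or non-disclosed; repeat negative | Withdraw | Table 6-2: keep. 8.9: silent on repeats | Yes, under A and B |
| 3. Visit 1 screen positive for a recreational or illicit drug | Withdraw | 8.9: withdraw. Table 6-2: no repeat | No |
| 4. Visit 1 laboratory abnormality judged clinically significant, not on the 8.9 Visit 1 list | Withdraw (mandatory) | 8.9: at most discretionary, and from treatment | Weak mismatch under A and B; the lists could be cumulative |
| 5. On treatment, ALT/AST at or above 3 x ULN confirmed and judged clinically significant, no 9.5 stopping criterion met | A: withdraw. B: does not apply | 9.5: follow closely, no required stop | Under A only |
| 6. On treatment, a 9.5 stopping criterion met, rechallenge then agreed | A: withdraw. B: does not apply | 9.5 and 8.9: may continue | Under A only |

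Cases 1 and 2 do not depend on the reading, because the drug-screen trigger is tied to Visit 1 either way. Case 1 is foreseeable: opioids are permitted acute treatment, and the protocol uses prescribed opioids as its own example in both 8.9 and Table 6-2.

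Case 5 can be made concrete. Take an asymptomatic, confirmed ALT of 4 x ULN at Week 16, with bilirubin, INR and eosinophils below the 9.5 thresholds. It is below the 5 x and 8 x ULN criteria, so 9.5 requires follow-up but does not require the drug to be stopped. If the investigator judges it clinically significant, reading A of 6.5.3 requires withdrawal from the study. Under reading B, 6.5.3 says nothing about it.

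For the exclusionary laboratory values, Section 4.3 was read item by item. It has no chemistry, hematology or serology limit. Its one test result of this kind is the urine pregnancy test, which 6.5.3 covers in a separate sentence. The numeric limits are in 8.9, labelled as withdrawal criteria.

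**The case against.** The best defence of the plan has three parts.

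**Table 6-2 belongs to 6.5.3.** The section ends by pointing to the table, so a site reading 6.5.3 through meets the exception. The two detailed passages agree on explained positives and use the same example. This stands as a reason not to say that sites do diverge; the documents show only that they could. It does not remove the contradiction. The prose is mandatory and unqualified, and it introduces the table only as a list of parameters.

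**The entry-rule reading is natural.** Exclusion criteria are assessed at Visit 1. The consequence of a positive pregnancy test in the same paragraph is tied to Visit 1. Section 8.9 groups the laboratory limits and the drug screen under a Visit 1 heading. On that reading 6.5.3 governs entry, 9.5 governs results after dosing, and the two do not overlap. The Medical Monitor must also be contacted for every confirmed ALT/AST elevation at or above 3 x ULN, which makes unnoticed divergence less likely for those cases. All of this stands, so a reader who infers that 6.5.3 flatly contradicts 9.5 goes further than the text allows. Reading A remains reasonable, because the preceding sentence covers any out-of-range value and the section covers samples from all scheduled visits.

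**The exclusionary-criteria wording is a labelling defect.** The limits in 8.9 lead to the same consequence, withdrawal, so no participant is shown to be withdrawn under one section and kept under another. This also stands: it is a pointer without a target, not a further conflict over disposition.

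**Conclusion.** The point holds in three parts of unequal strength.

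- **Drug screen: firm.** Section 6.5.3 contradicts 8.9 and Table 6-2 on any reading. The rule is wrong as written in at least one place.
- **Visit scope: conditional.** The sentence is ambiguous. Under reading A it conflicts with 9.5 and with the discretionary clause in 8.9. Under reading B there is no conflict with 9.5.
- **Exclusionary values: minor.** The reference has no numeric target in 4.3.

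The number of participants affected cannot be computed, because the documents give no rate of positive screens or of clinically significant abnormalities. A reader might be tempted to size it. Assuming, without support in the documents, that 1% to 5% of about 750 participants have an explained positive gives 750 x 0.01 = 7.5 to 750 x 0.05 = 37.5, or roughly 8 to 38. That would be the number exposed to the contradiction, not the number handled in opposite ways, which depends on how the approximately 110 sites read the text and could be zero. Likewise, 750 x 10 on-treatment visits = 7,500 laboratory panels matters only under reading A. It is a ceiling that assumes full enrolment, no dropout and no remote visits, and remote visits collect no laboratory samples.

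The 22 February 2019 protocol contains the same wording in these sections, and Amendment 1 did not change it. This is an internal inconsistency worth correcting, not evidence that any result is biased.

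**What to change.** The sponsor should:

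1. Reconcile the drug-screen rule so that the prose of 6.5.3, Table 6-2 and 8.9 say the same thing, including whether a negative repeat is enough, on which 8.9 is silent.
2. State in 6.5.3 the visit or visits to which each of the three triggers applies, and reconcile the clinically-significant trigger with 9.5 and with the any-visit clauses of 8.9.
3. Correct the reference to exclusionary laboratory values so that it points to limits that exist in the protocol.
4. Send sites a clarification letter with the reconciled text.

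Which rule should prevail is for the sponsor to decide; this review does not say. The cost is protocol wording and one letter. No procedure, visit or analysis is added.
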